## Summary of Changes to the Protocol

The previous version of this protocol (Version 1.0, 29 May 2019) was amended to create the current version (Version 1.4 US, 08 March 2021). The protocol history is provided below.

Protocol History	
Version and Date of Protocol	Comments
Version 1.0, 29 May 2019	Original version
Version 1.4 US, 08 March 2021	Current version Protocol amended to include an optional at-home sweat chloride sample collection.

Key changes in the current version of the protocol are summarized below.

Change and Rationale	Affected Sections
Added an optional at-home sweat chloride sample collection for approximately 50 subjects.	Section 11.5.1

[figure not shown]
Typographical and administrative changes were also made to improve the clarity of the document.

## 2 PROTOCOL SYNOPSIS

Title	A Phase 3, Open-label Study Evaluating the Long-term Safety of VX-445 Combination Therapy in Subjects With Cystic Fibrosis
Brief Title	A Study Evaluating the Long-term Safety of VX-445 Combination Therapy
Clinical Phase and Clinical Study Type	Phase 3, safety
Objectives	
Primary Objective
 
To evaluate the long-term safety and tolerability of VX-445/tezacaftor (TEZ)/ivacaftor (IVA)

Endpoints	
Primary Endpoint
 
Safety and tolerability of long-term treatment with VX-445/TEZ/IVA based on adverse events (AEs), clinical laboratory values, ECGs, vital signs, pulse oximetry, and spirometry
 
Other Endpoint
 
Sweat chloride

Number of Subjects	Over 400 subjects are expected to enroll in this study.
Study Population	Male and female subjects with cystic fibrosis who are 12 years of age or older and homozygous or heterozygous for the F508del mutation
Investigational Drug	
Study drug refers to VX-445/TEZ/IVA and IVA.
 
Study drugs will be orally administered as 2 fixed-dose combination film-coated tablets (VX-445/TEZ/IVA) in the morning and as 1 film-coated IVA tablet in the evening.
 
Active substance: VX-445, TEZ (VX-661), and IVA (VX-770)
 
Activity: VX-445 is a CFTR corrector, TEZ is a CFTR corrector, and IVA is a CFTR potentiator (increased Cl secretion)
 
Strength: 100 mg/50 mg/75 mg FDC tablet
 
Active substance: IVA (VX-770)
 
Activity: CFTR potentiator (increased Cl secretion)
 
Strength: 150 mg

Study Duration	The total study duration is up to approximately 100 weeks (from the first dose of study drug in this study), including a Treatment Period of up to 96 weeks and a 4-week Safety Follow-up Period.

**Study Design** This is a Phase 3, multicenter, open-label study for subjects in Study 659-105, a Phase 3 Vertex study investigating VX-659/TEZ/IVA, who meet eligibility criteria. All subjects will receive the triple combination of VX-445/TEZ/IVA at the same dose level as that evaluated in the VX-445 Phase 3 pivotal trials.

### VX18-445-113 Study Design

IVA: ivacaftor; q12h: every 12 hours; qd: once daily; TEZ: tezacaftor

Note: Figure is not drawn to scale.

a All subjects will receive VX-445 200 mg qd, TEZ 100 mg qd, and IVA 150 mg q12h.

**Assessments** **Safety:** AEs, clinical laboratory assessments, ECGs, vital signs, height, weight, pulse oximetry, physical examinations, spirometry, and ophthalmologic examinations (the latter for subjects <18 years of age on the date of informed consent in the parent studies of Study 659-105)

**Other:** Sweat chloride

**Statistical Analyses** The primary objective of the study is the evaluation of the long-term safety and tolerability of VX-445/TEZ/IVA. The safety endpoints include AEs, clinical laboratory values, ECGs, vital signs, pulse oximetry, and spirometry from the first dose of study drug in this study, for subjects who received at least 1 dose of study drug in this study. The safety analysis will be descriptive only.

**Interim Analyses** Interim analyses may take place at any time during the study at the discretion of the sponsor.

**IDMC Reviews** The independent data monitoring committee (IDMC) will conduct periodic safety reviews of study data as outlined in the IDMC charter.

### **3 SCHEDULE OF ASSESSMENTS**

The schedule of assessments is provided in [Table 3-1](#). All visits will be scheduled relative to the Day 1 Visit in this study.

Assessments may be performed in any order when more than 1 assessment is required at a particular time point. All assessments will be performed before study drug dosing (Section 9.6.1), unless noted otherwise.

**Table 3-1 VX18-445-113: Treatment Period and Safety Follow-up Visit**

Event/Assessment a	Treatment Period							ETT Visit b	Safety Follow-up Visit (28 ± 7 Days After Last Dose) c	Comments
	Day 1 d	Day 15 (± 3 Days)	Weeks 4, 8, 16, 24, 36 (± 5 Days)	Weeks 12, 20, 28, 32, 40, 44, 52, 56, 64, 68, 76, 80, 88, 92 (± 5 Days)	Week 48 (± 5 Days)	Weeks 60, 72, 84 (± 5 Days)	Week 96 (± 5 Days)			
Clinic visit	X	X	X		X	X	X	X	X	
Telephone contact				X						Results of a home urine pregnancy test will be reported to the site by telephone (Section 11.4.2).
ICF and assent (when applicable)	X									
Inclusion and exclusion criteria confirmation	X									Section 8
Height and weight	X		X		X	X	X	X	X	Measured with shoes off. For subjects whose date of informed consent occurs after their 21 st birthday, height will be collected only at the Day 1 Visit (Section 11.4.4).

a All assessments will be performed before study drug dosing unless noted otherwise (Section 9.6.1).

b If the subject prematurely discontinues study drug treatment, an ETT Visit should be scheduled as soon as possible after the decision to discontinue treatment (Section 9.1.3).

c The Safety Follow-up Visit is required for all subjects unless otherwise specified. Refer to Section 9.1.2 for subjects who transition to a commercially available or managed access program-supplied next-generation corrector TC regimen. For subjects who complete an ETT Visit 3 weeks or later following the last dose of study drug, the ETT Visit will replace the Safety Follow-up Visit (Section 9.1.3).

d The Day 1 Visit should occur on the same day as the ETT Visit of Study 659-105 (Section 9.1.1).

**Table 3-1 VX18-445-113: Treatment Period and Safety Follow-up Visit**

Event/Assessment a	Treatment Period							ETT Visit b	Safety Follow-up Visit (28 ± 7 Days After Last Dose) c	Comments
	Day 1 d	Day 15 (± 3 Days)	Weeks 4, 8, 16, 24, 36 (± 5 Days)	Weeks 12, 20, 28, 32, 40, 44, 52, 56, 64, 68, 76, 80, 88, 92 (± 5 Days)	Week 48 (± 5 Days)	Weeks 60, 72, 84 (± 5 Days)	Week 96 (± 5 Days)			
Ophthalmologic examination					X		X	X	X	Subjects <18 years of age on the date of informed consent in the parent studies of Study 659-105 will have an ophthalmologic examination within 28 days of the Week 48 and Week 96 Visits. In addition, an ophthalmologic examination will be performed within 28 days of the ETT Visit for subjects who prematurely discontinue study drug if the subject has received at least 12 weeks of study drug since their last ophthalmologic examination. (Section 11.4.7).
Complete physical examination	X						X	X		Section 11.4.3
Pregnancy test	Urine		Urine	Urine	Urine	Urine	Serum	Serum	Serum	All female subjects (Section 11.4.2)
FSH										As needed for any suspected postmenopausal female with at least 12 months of continuous spontaneous amenorrhea (Section 11.4.2)
Standard 12-lead ECG	X	X	Weeks 8, 24		X	Week 72	X	X	X	After subjects have rested for at least 5 minutes and before dosing, as applicable (Sections 11.4.3, 11.4.5, and 11.4.6)
Vital signs	X	X	X		X	X	X	X	X	
Pulse oximetry	X	X	X		X	X	X	X	X	
Spirometry	X	X	X		X	X	X	X	X	Section 11.4.8
SwCl			Week 24				X	X		Approximately 50 subjects may participate in 1 to 2 additional, optional sweat tests at unscheduled home visits (Section 11.5.1)
Urinalysis	X				X		X	X	X	Section 11.4.2

**Table 3-1 VX18-445-113: Treatment Period and Safety Follow-up Visit**

Event/Assessment a	Treatment Period							ETT Visit b	Safety Follow-up Visit (28 ± 7 Days After Last Dose) c	Comments
	Day 1 d	Day 15 (± 3 Days)	Weeks 4, 8, 16, 24, 36 (± 5 Days)	Weeks 12, 20, 28, 32, 40, 44, 52, 56, 64, 68, 76, 80, 88, 92 (± 5 Days)	Week 48 (± 5 Days)	Weeks 60, 72, 84 (± 5 Days)	Week 96 (± 5 Days)			
Hematology	X	X	X		X	X	X	X	X	
Coagulation	X		Week 24		X	Week 72	X	X	X	
Serum chemistry	X	X	X		X	X	X	X	X	
Study drug count	X	X	X		X	X	X	X		Section 10.6
Study drug dosing	Day 1 through evening before Week 96 Visit									Subjects on study drug interruption from Study 659-105 may NOT begin dosing until they meet the criteria in Section 9.8. Refer to Section 9.6.1 for study drug administration details.
Medications review	Continuous from signing of the ICF (or assent form) through completion of study participation									Completion of study participation is defined in Section 9.1.5.
Treatments and procedures review	Continuous from signing of the ICF (or assent form) through completion of study participation									
AEs and SAEs	Continuous from signing of the ICF (or assent form) through completion of study participation									

AE: adverse event; ETT: Early Termination of Treatment; FSH: follicle-stimulating hormone; ICF: informed consent form; SAE: serious adverse event; SwCl: sweat chloride

## List of Abbreviations

Abbreviation	Definition
AE	adverse event
ALT	alanine transaminase
AST	aspartate transaminase
BMI	body mass index
bpm	beats per minute
CF	cystic fibrosis
CFTR	CF transmembrane conductance regulator protein
CFTR	CF transmembrane conductance regulator gene
CRF	case report form
CSR	clinical study report
CTCAE	Common Terminology Criteria for Adverse Events
CYP	cytochrome P450
ECG	electrocardiogram
EDC	electronic data capture
ETT	Early Termination of Treatment
EU	European Union
F508del	CFTR gene mutation with an in-frame deletion of a phenylalanine codon corresponding to position 508 of the wild-type protein
FDA	Food and Drug Administration
FDC	fixed-dose combination
FEF 25%-75%	forced expiratory flow, midexpiratory phase
FEV 1	forced expiratory volume in 1 second
FSH	follicle-stimulating hormone
FVC	forced vital capacity
GCP	Good Clinical Practice
GPS	Global Patient Safety
HIPAA	Health Insurance Portability and Accountability Act
HR	heart rate
ICF	informed consent form
ICH	International Council for Harmonization
IDMC	independent data monitoring committee
IEC	independent ethics committee
IND	Investigational New Drug (application) (US)
IPD	important protocol deviation
IRB	institutional review board
IVA	ivacaftor
LUM	lumacaftor
max	maximum value
MedDRA	Medical Dictionary for Regulatory Activities
MF	minimal function
min	minimum value
n	number of subjects

Abbreviation	Definition
OATP	organic anion transporting polypeptide
PE	physical examination
P-gp	P-glycoprotein
ppFEV 1	percent predicted forced expiratory volume in 1 second
PR	PR interval, segment
PT	Preferred Term
q12h	every 12 hours
qd	once daily
QRS	the portion of an ECG comprising the Q, R, and S waves, together representing ventricular depolarization
QT	QT interval
QTc	QT interval corrected
QTcF	QT interval corrected by Fridericia's formula
RR	interval from the onset of 1 QRS complex to the next
SAE	serious adverse event
SAP	statistical analysis plan
SD	standard deviation
SI	SI units (International System of Units)
SOC	System Organ Class
SwCl	sweat chloride
TC	triple combination
TE	treatment-emergent
TEAE	treatment-emergent adverse event
TEZ	tezacaftor
ULN	upper limit of normal
US	United States

## 5 INTRODUCTION

### 5.1 Background

Cystic fibrosis (CF) is an autosomal recessive chronic disease with serious morbidities and frequent premature mortality. CF affects more than 70,000 individuals worldwide (approximately 30,000 in the US and 45,000 in the EU). Based on its prevalence, CF qualifies as an orphan disease.

CF is caused by decreased quantity and/or function of the CFTR protein due to mutations in the *CFTR* gene. CFTR is an ion channel that regulates the flow of chloride and other ions across epithelia in various tissues, including the lungs, pancreas and other gastrointestinal organs, and sweat glands. Decreased CFTR quantity or function results in the failure to regulate chloride transport in these tissues leading to the multisystem pathology associated with CF. In the lungs, obstruction of airways with thick mucus, establishment of a chronic bacterial infection in the airways, and damaging inflammatory responses are all thought to play a role in causing irreversible structural changes in the lungs, leading to respiratory failure. Progressive loss of lung function is the leading cause of mortality.

The most common disease-causing *CFTR* mutation is *F508del*, which accounts for approximately 70% of the identified alleles in people with CF. Approximately 40% to 45% of people with CF are homozygous for *F508del* (F/F), and approximately 85% have at least 1 *F508del* allele.

Based on the understanding of the molecular defects caused by *CFTR* mutations, 2 complementary approaches have been developed to address the decreased quantity and/or function of CFTR in order to enhance chloride transport in patients with CF. Correctors facilitate the cellular processing and trafficking to increase the quantity of CFTR at the cell surface. Potentiators increase the channel open probability (channel gating activity) of the CFTR protein delivered to the cell surface to enhance ion transport. With differing mechanisms of action, a combination of correctors and potentiators increases *F508del* CFTR-mediated chloride transport more than either type of modulator alone.

The therapeutic activity of CFTR modulators has been established with products developed by Vertex and approved for the treatment of CF: ivacaftor (IVA) monotherapy (Kalydeco™), lumacaftor (LUM)/IVA (Orkambi®), and tezacaftor (TEZ)/IVA (Symdeko™/Symkevi®).

VX-445 is a next-generation CFTR corrector. In vitro, the triple combination (TC) of VX-445, TEZ, and IVA (VX-445/TEZ/IVA) increased CFTR chloride transport more than any of the dual combinations (VX-445/TEZ, VX-445/IVA, and TEZ/IVA) or individual components (VX-445, TEZ, and IVA) when added to human bronchial epithelial cells derived from 2 groups of patients with CF: those heterozygous for *F508del* with a second *CFTR* allele carrying a minimal function (MF) mutation that is not responsive to TEZ, IVA, and TEZ/IVA (F/MF genotypes); and those homozygous for *F508del* (F/F genotypes).

Additional information about VX-445/TEZ/IVA can be found in the Investigator's Brochure.

### 5.2 Study Rationale

The study will provide data on the long-term safety and tolerability of VX-445/TEZ/IVA in subjects with CF who are homozygous or heterozygous for the *F508del* mutation.

Subjects who participated in Study VX17-659-105 and meet eligibility criteria are eligible to enroll. Study 659-105 is an open-label study that enrolled subjects who completed the last Treatment Period visit in a parent study. Parent studies were two Phase 3 pivotal studies investigating VX- 659 in combination with TEZ and IVA. Study VX17-659-102 enrolled F/MF subjects, and Study VX17-659-103 enrolled F/F subjects.

## **6 STUDY OBJECTIVES**

### **6.1 Primary Objective**

To evaluate the long-term safety and tolerability of VX-445/TEZ/IVA

## **7 STUDY ENDPOINTS**

### **7.1 Primary Endpoint**

Safety and tolerability of long-term treatment with VX-445/TEZ/IVA based on adverse events (AEs), clinical laboratory values, ECGs, vital signs, pulse oximetry, and spirometry

### **7.2 Other Endpoint**

Sweat chloride

## **8 STUDY POPULATION**

Eligibility will be reviewed and documented by an appropriately qualified member of the investigator's team before subjects are enrolled.

Subjects who meet all of the inclusion criteria and none of the exclusion criteria will be eligible.

### **8.1 Inclusion Criteria**

1. Subject (or his or her legally appointed and authorized representative) is willing to sign and date an informed consent form (ICF), and, when appropriate, an assent form.
2. Willing and able to comply with scheduled visits, treatment plan, study restrictions, laboratory tests, contraceptive guidelines, and other study procedures.
3. Currently participating in Study 659-105. Current participation is defined as one of the following:
  - On study drug treatment in Study 659-105 as of the day prior to the Day 1 Visit in this study.
  - On study drug interruption in Study 659-105 as of the day prior to the Day 1 Visit in this study.

Subjects who permanently discontinue VX-659/TEZ/IVA in Study 659-105 for any reason other than enrolling into this study are not eligible.

4. Willing to remain on a stable CF treatment regimen (as defined in Section 9.5) through completion of study participation.

## 8.2 Exclusion Criteria

1. History of any comorbidity that, in the opinion of the investigator, might confound the results of the study or pose an additional risk in administering study drug to the subject.
2. Pregnant and nursing females. All female subjects must have a negative pregnancy test at the Day 1 Visit before receiving the first dose of study drug.
3. History of drug intolerance in Study 659-105 that would pose an additional risk to the subject in the opinion of the investigator (e.g., subjects with a history of allergy or hypersensitivity to VX-659/TEZ/IVA).
4. Current participation in an investigational drug trial (other than Study 659-105). Participation in a noninterventional study (including observational studies, registry studies, and studies requiring blood collections without administration of study drug) and screening for another Vertex study is permitted.

## 9 STUDY IMPLEMENTATION

### 9.1 Study Design

This is a Phase 3, multicenter, open-label study for subjects in Study 659-105, a Phase 3 Vertex study investigating VX-659/TEZ/IVA, who meet eligibility criteria (Section 8).

[figure not shown]
A schematic of the study design is shown in Figure 9-1.

All subjects will receive a TC of VX-445/TEZ/IVA at the same dose level as that evaluated in the VX-445 Phase 3 pivotal trials (VX-445 200 mg qd, TEZ 100 mg once daily [qd], and IVA 150 mg every 12 hours [q12h]). Study drug administration is described in Section 9.6.

Study visits and assessments to be conducted are shown in Table 3-1. All visits will occur within the windows specified.

Study drug is defined in Section 10.

**Figure 9-1 VX18-445-113 Study Design**

IVA: ivacaftor; q12h: every 12 hours; qd: once daily; TEZ: tezacaftor

Note: Figure is not drawn to scale.

a All subjects will receive VX-445 200 mg qd, TEZ 100 mg qd, and IVA 150 mg q12h.

#### 9.1.1 Treatment Period

Treatment Period assessments are listed in Table 3-1.

The Day 1 Visit should occur on the same day as the ETT Visit of Study 659-105. Subjects will receive the first dose of study drug on Day 1 after obtaining informed consent (and assent, when

applicable) and confirming eligibility, and completing any pre-dose assessments. Subjects who enroll in this study on a drug interruption will complete Day 1 assessments but will NOT receive the first dose of study drug until they meet the resumption criteria in Section 9.8; before receiving study drug, subjects will repeat all Day 1 assessments (Section 11.4).

Administration details are provided in Section 9.6.

### **9.1.2 Safety Follow-up**

The Safety Follow-up Visit is scheduled to occur 28 ( $\pm$  7) days after the last dose of study drug. The Safety Follow-up Visit assessments are listed in Table 3-1.

The Safety Follow-up Visit is required for all subjects. However, subjects who transition within 28 days of the last dose of study drug to either a commercially available or managed access program-supplied next-generation corrector TC regimen, or to another qualified Vertex study will complete the Week 96 Visit (or the Early Termination of Treatment [ETT] Visit, if the transition occurs before the Week 96 Visit). In these cases, the Week 96 Visit (or the ETT Visit) will replace the Safety Follow-up Visit.

For subjects who complete an ETT Visit 3 weeks or later following the last dose of study drug, the ETT Visit will replace the Safety Follow-up Visit (Section 9.1.3).

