### **9.1.5 Completion of Study Participation**

Completion of study participation for each individual subject is defined as: the Safety Follow-up Visit; or, in situations in which the ETT Visit or the Week 96 Visit replace the Safety Follow-up Visit (Section 9.1.2), the ETT Visit, or the Week 96 Visit.

If subjects withdraw consent or assent, completion of study participation is defined as date of withdrawal of consent or assent, whichever is earlier (Section 9.9).

If subjects are lost to follow-up (Section 9.1.4), the date of completion of study participation will be defined as the date of last contact.

The end of study is defined in Section 13.2.8.

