## 9.9 Removal of Subjects

Subjects may withdraw from the study at any time at their own request. Subjects may be withdrawn from study drug treatment at any time at the discretion of the investigator or Vertex for safety, behavior, noncompliance with study procedures, or administrative reasons.

In addition, a subject must be discontinued from study drug treatment if the subject meets any of the following criteria:

- Meets any of the stopping (discontinuation) criteria (Section 9.8)
- Becomes pregnant (Section 11.4.9.2)

If a subject does not return for a scheduled visit, reasonable effort will be made to contact the subject. In any circumstance, reasonable effort will be made to document subject outcome. The investigator will inquire about the reason for withdrawal, request that the subject return all unused investigational product(s), request that the subject return for an ETT Visit and Safety Follow-up Visit, if applicable (Section 9.1.2), and follow up with the subject regarding any unresolved AEs.

If the subject withdraws consent or assent for the study, no further assessments will be performed. Vertex may retain and continue using the study data and samples after the study ends, and may use the samples and information in the development of the study compounds, and for other drugs and diagnostics, in publications and presentations, and for education purposes. If the subject withdraws from the study, the study data and samples collected will remain part of the study. A subject will not be able to request the withdrawal of his or her information from the study data. A subject may request destruction of the samples collected from him or her during the study as long as those samples can be identified as his or her samples.

With the exception of subjects who cannot access the commercial product after regulatory approval because reimbursement by the subject's insurance carrier (whether government or private payer) is not yet available or because the subject lacks insurance coverage, subjects who become eligible to receive commercially available VX-445/TEZ/IVA by prescription of a physician may be discontinued from study drug dosing and will complete the ETT Visit before beginning commercially available VX-445/TEZ/IVA dosing. The Safety Follow-up Visit will not be required if the subject immediately continues on commercially available VX-445/TEZ/IVA.

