### 12.3 Statistical Analysis

#### 12.3.1 General Considerations

**Continuous variables** will be summarized using the following descriptive summary statistics: the number of subjects (n), mean, SD, median, minimum value (min), and maximum value (max). The precision of the measurement for each continuous variable will be specified in the SAP. Unless otherwise specified, min and max values will be reported with the same precision as the units of the raw data. The mean, median, and SD will be reported to 1 additional decimal

place. Any values that require a transformation to standard units (metric or SI) will be converted with the appropriate precision.

**Categorical variables** will be summarized using counts and percentages. Percentages will be presented to 1 decimal place.

**The baseline value**, unless otherwise specified, for the long-term safety analysis will be the most recent non-missing measurement (scheduled or unscheduled) collected before the first dose of VX-445/TEZ/IVA in this study. For assessments collected in duplicate or triplicate, the baseline will be defined as the average of non-missing values.

**Change (absolute change)** from baseline will be calculated as post-baseline value - baseline value.

The **Treatment-emergent (TE) Period** in this study will include the time from the first dose of study drug in this study to 28 days after the last dose of study drug in this study or to the completion date of study participation (defined in Section 9.1.5), whichever occurs first.

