### **13.1.1.3 Documentation of Adverse Events**

All AEs will be collected from the time the ICF is signed until the subject completes study participation, as defined in Section 9.1.5.

All subjects will be queried, using nonleading questions, about the occurrence of AEs at each study visit. When possible, a constellation of signs and/or symptoms will be identified as 1 overall event or diagnosis. All AEs for enrolled subjects will be recorded in the CRF and source document. The following data will be documented for each AE:

- Description of the event
- Classification of "serious" or "nonserious"
- Date of first occurrence and date of resolution (if applicable)
- Severity
- Causal relationship to study drug(s)
- Action taken
- Outcome
- Concomitant medication or other treatment given

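### Sections 9.1.2 and 9.9 state different conditions for waiving the Safety Follow-up Visit; separately, when that visit is replaced, AE collection and the TE Period stop at the ETT or Week 96 Visit, so an off-drug gap before the next regimen is not covered

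*Protocol*

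**What the plan says.** **The waiver.** Protocol Section 9.1.2 makes the Safety Follow-up Visit the default for everyone, 28 ± 7 days after the last dose. It then makes an exception for "subjects who transition within 28 days of the last dose of study drug to either a commercially available or managed access" next-generation triple combination, or to another qualified Vertex study, and adds: "In these cases, the Week 96 Visit (or the ETT Visit) will replace the Safety Follow-up Visit".

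Section 9.9 addresses subjects who gain access to commercial drug. Such a subject "will complete the ETT Visit before beginning commercially available VX-445/TEZ/IVA dosing", and then: "The Safety Follow-up Visit will not be required if the subject immediately continues on commercially available VX-445/TEZ/IVA".

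**Cross-references.** Table 3-1 footnote c sends transitioning subjects to Section 9.1.2. Section 9.9, on withdrawals, tells the investigator to "request that the subject return for an ETT Visit and Safety Follow-up Visit, if applicable (Section 9.1.2").

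**The cut-offs.**
- Section 9.1.5 makes the Safety Follow-up Visit the completion of participation, but "in situations in which the ETT Visit or the Week 96 Visit replace the Safety Follow-up Visit" that earlier visit is completion instead.
- Section 13.1.1.3: "All AEs will be collected from the time the ICF is signed until the subject completes study participation, as defined in Section 9.1.5".
- Section 12.3.1 ends the TE Period at "28 days after the last dose of study drug in this study or to the completion date of study participation", whichever is first. SAP Section 8.1 repeats this rule for Part A and for Part B.

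**The concern.** There are two separate problems.

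The first is wording. One section allows a gap of up to 28 days and several destinations; the other names immediate continuation on one product. A site planning follow-up for a subject who will start commercial drug some days after the last study dose could plan differently depending on which section it works from.

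The second affects the data and does not depend on the first. The primary endpoint is safety and tolerability. A subject who has the follow-up visit is observed for at least three weeks after the last dose. A subject whose visit is replaced stops contributing at the ETT or Week 96 Visit, even if the next regimen starts weeks later. Whether new events after stopping enter the database, and count as treatment-emergent, then depends on the subject's route to the next regimen.

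**Working it through.** **1. The two conditions side by side**

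| | Section 9.1.2 | Section 9.9 |
|---|---|---|
| Timing | Transition within 28 days of last dose | Immediate continuation |
| Destination | Commercial or managed-access triple combination, or another Vertex study | Commercial VX-445/TEZ/IVA |
| Commercial drug, no gap | Visit replaced | Visit not required |
| Commercial drug from day 20, ETT on day 1 | Visit replaced | Condition not met; the section does not say what follows |
| Commercial drug after day 28, ETT before day 21 | Exception does not apply; visit required | Condition not met; default applies |

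The sections agree in the third and fifth rows. Only the fourth, a short gap inside 28 days, can be read two ways. A different reading there needs Section 9.9 to be combined with the default of a required visit.

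**2. The cut-off chain.** Visit replaced (9.1.2) → ETT or Week 96 Visit is completion (9.1.5) → AE collection ends there (13.1.1.3) → TE Period ends there, because completion precedes day 28 (12.3.1, SAP 8.1). Section 9.9 plays no part in this chain.

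**3. Length of the uncovered gap**

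Inputs: last study dose = day 0; ETT or Week 96 Visit on day *e*; first dose of the next regimen on day *s*, with *s* ≤ 28 (Section 9.1.2). Wholly off-drug days are 1 to *s* − 1. Those after the visit number

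uncovered days = *s* − 1 − *e*.

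At the limit *s* = 28 this is 27 − *e*:

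| ETT day *e* | Uncovered days |
|---|---|
| 0 (day of last dose) | 27 |
| 1 | 26 |
| 7 | 20 |
| 14 | 13 |
| 20 | 7 |

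- Table 3-1 ends dosing the evening before the Week 96 Visit, so for completers *e* = 1 and the maximum is 26.
- If within 28 days is read to exclude day 28, each figure falls by 1.
- In the fourth-row example (*s* = 20, *e* = 1) the result is 20 − 1 − 1 = 18 days.
- With no gap (*s* = 1) the result is 0.
- An ETT Visit on day 21 or later replaces the follow-up visit in any case (9.1.2, 9.1.3), so the waiver conditions no longer matter.

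**4. Comparison with a subject who has the visit.** The visit window is 28 − 7 = day 21 to 28 + 7 = day 35. The TE Period then ends at the earlier of day 28 and the visit, that is, between days 21 and 28. For a Week 96 completer whose visit is replaced, it ends on day 1.

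**5. The plan's own statistical figure.** Protocol 12.1 says that zero events in over 400 subjects rule out a frequency above 1% with 95% confidence. With n = 400, 1 − 0.05^(1/400) = 0.75% (one-sided) and 1 − 0.025^(1/400) = 0.92% (two-sided). The statement reproduces, and the point made here does not depend on it.

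**The case against.** **Do the two sections contradict each other?** A reader might infer that they give opposite answers. The documents do not support that. Section 9.9 says the visit is not required if the subject continues immediately; it does not say only if, and it nowhere requires a visit after a gap. Its condition falls inside the 28-day window of 9.1.2, and its single product is a subset of the 9.1.2 list. Two cross-references point to 9.1.2 as the governing section. What remains is that, if 9.1.2 governs, the word for immediacy in 9.9 does no work and invites a different reading.

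**Does the mismatch cause the missing days?** A reader might also infer this. It does not: the uncovered days follow from 9.1.2 and the cut-offs and would exist if 9.9 were deleted. So aligning the two sections need not close the gap.

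**Is the site left with only days 28–35 for the visit if a planned switch falls through?** No. The window opens on day 21, and nothing prevents a site from scheduling the visit and holding it before day 28 if no switch has occurred.

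**Are all events lost?** No. Section 13.1.2.2 keeps related SAEs reportable after the Safety Follow-up Visit, Section 13.1.1.7 follows AEs to a final outcome, and Section 9.9 asks for follow-up of unresolved AEs. But the last two concern events already recorded. The first is tied to a visit these subjects do not have, does not say how it applies when the visit is replaced, and omits non-serious and unrelated events.

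**Is the cut-off simply a design choice?** It is explicit and consistent between protocol and SAP. That is a fair defence where the subject continues without a gap; it is weaker where the subject is off drug for up to several weeks in a study whose endpoint is safety.

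**Conclusion.** The point holds in two limited parts.

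- **Wording:** the waiver conditions in 9.1.2 and 9.9 are not aligned and need to be reconciled. They are not opposite rules.
- **Data:** for a subject whose visit is replaced and who has an off-drug gap, new events after the ETT or Week 96 Visit are neither collected nor treatment-emergent, except possibly related SAEs.

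The uncovered time is at most 26 days for Week 96 completers. The 27-day ceiling needs both an ETT Visit on the day of last dose and a start on day 28. These limits assume that day 28 counts as within 28 days. Many switchers may have no gap at all. The documents give neither the number of switchers nor the length of any gap, so a count of affected subjects, or an effect on TEAE frequencies, cannot be estimated from them.

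This should be corrected because the endpoint is safety and the correction is cheap. Confidence is high in the differing conditions and the cut-off chain, and low in how many subjects they touch.

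**What to change.** 1. **Reconcile the waiver.** Make Section 9.1.2, Section 9.9 and Table 3-1 footnote c state one condition: the same timing and the same list of qualifying regimens. Which visit rule applies is for the sponsor to decide.
2. **Separate observation from the visit.** In Protocol 9.1.5, 12.3.1 and 13.1.1.3 and in SAP 8.1, for subjects whose follow-up visit is replaced on transition, run AE collection and the TE Period to the earlier of the first dose of the next regimen and 28 days after the last study dose. Change both together: extending only the TE Period would add days on which no event could be recorded.
3. **Clarify the backstop.** State in 13.1.2.2 how reporting of related SAEs applies when the Safety Follow-up Visit has been replaced.

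The cost is protocol and SAP wording, recording the start date of the next regimen, and AE recording, for example by telephone, for subjects with a gap. Subjects who continue without a gap need no additional AE follow-up.
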